HPV31/33/35/39/45/51/52/53/56/58/59/66/68 for exploratory aims. Participants positive for high-risk HPV and/or HPV6/11 on any sample will have a 6-12 month follow-up visit to measure HPV type-specific persistence - a surrogate endpoint recommended by the WHO (87). At young ages, the risk of precancer is very low, but for safety purposes, participants will be offered colposcopy if they have a persistent high-risk HPV cervical infection and anoscopy if they have a persistent HPV16/18 anal infection. Main outcomes will be prevalence and 6-12 month type-specific persistence of cervicovaginal (as an excellent proxy for cervical sampling (87)), anal, and/or oral infections by HPV6/11/16/18 as well as antibody titers for HPV6/11/16/18. Cervical and anal biopsy specimens diagnosed as CIN2+ or AIN2+, respectively, will also be tested for the 15 high-risk and 2 low-risk HPV types for secondary outcomes. In an exploratory aim, we will examine risk factors, including the cervicovaginal microbiome (88), for HPV type-specific persistence in WLWH and HIV[-] women.

At enrollment, blood will be collected for plasma from all participants. In the study laboratory, a stratified random sample of specimens will be selected to measure by ELISA anti-HPV16 and -HPV18 antibody titers and compare HPV-vaccinated WLWH. We will test titers in at least 1,302 samples ($n \geq 548$, 50% with three doses and 50% with two doses of Gardasil®, for both HPV-vaccinated WLWH and for HPV-vaccinated HIV[-] women; $n \geq 108$ for both HPV-vaccinated WLWH and for HPV-vaccinated HIV[-] women as controls) and up to 3,028 samples.

VI.B. Study Locations

In Kigali, the study staff will work with five public clinics that participate in the International Epidemiology Databases to Evaluate AIDS (IeDEA) program and the WE-ACTx private clinic (**Table 2**). Study investigators and staff successfully worked with these clinics in a cervical cancer screening study of 5,000 WLWH (83). If needed, the staff will work with up to four other public health clinics to recruit additional participants.

Table 2. Study enrollment sites	
IeDEA Sites	Non-IeDEA sites
1. Busanza health center (HC)	1. Cor-unum HC

2. Gikondo HC 3. Kicukiro HC 4. Nyarugunga HC 5. Rwanda Military Hospital 6. WE-ACTx private clinic	2. Kacyiru HC 3. Remera HC 4. Rwampara HC
---	---

VI.C. Target Population

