Using the variance of GMT for HPV antibodies from Einstein et al. (111, 112), a sample size of at least 274 will provide 80% power ($p=0.05$) to detect a 30% difference in GMT between HPV-vaccinated WLWH and HIV[-] women for a given number of doses. If there is no appreciable difference in the titers between those who got 3 or two doses, we can combine those groups with different doses. In that case, with a sample size of at least 548, there will be 80% power ($p=0.05$) to detect a 22% difference between HPV-vaccinated WLWH and HIV[-] women.

VII.C. Exploratory Aim: A Study of 6-12 Month Type-Specific HPV Persistence

Given the size of the cohort of WLWH (n=1,514 at baseline), the planned follow-up of the HPV-positive WLWH, and the laboratory assay capacities that are available and will be

developed at the study lab, we have unique opportunity to look at determinants of early, short-term HPV genotype-specific persistence/clearance in young women. Studies of HPV persistence in WLWH, especially in SSA, are limited in number and size (113-120). There is a growing body of evidence that an altered CVM (cervicovaginal dysbiosis) is associated with persistent HPV infection (86) but there are no published data on its role in HPV persistence in WLWH. There is evidence of greater cervicovaginal microbiotic diversity in WLWH compared to HIV[-] women (121) and a complex, possible inter-dependence of CVM and HPV natural history (122). Given the importance of short-term HPV persistence as a biomarker of cervical-cancer risk (123) as well as an endpoint for prophylactic HPV vaccine trials, this is a unique opportunity to understand its determinants.

Paired baseline and follow up specimens from participants whose baseline cervicovaginal specimen tests HPV positive will have their cervicovaginal microbiome characterized. We will examine factors such as baseline and history (if available) of HIV disease status (HIV viral load and CD4), the presence of the HPV genotype at other anatomic sites, CVM composition, and other risk factors (e.g., sexual behaviors) on whether HPV infection persists vs. clears.

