APPENDIX III. ENROLLMENT QUESTIONNAIRE

Thank you for agreeing to participate in our study. This interview should take no more than 20 minutes. Some of these questions are personal about your life, your reproductive health, and your sexual history. All your answers are strictly confidential, and it is very important for us that you try to answer all the questions as openly as possible, even if they are a little uncomfortable or embarrassing. This information will be important in understanding how the HPV vaccine protects women against HPV infection. If you don't understand any of the questions, please inform the study nurse who will try to help explain them. You should also be aware that you have a right not to respond to any question with which you are uncomfortable.

A. Socio-demographics

1. What is your date of birth? DD/ MM /YYYY (enter all 0 if not remembered)

__ / __ / __ __

2. What is your age? __ (Year)

3. What is your marital status?

- Married/Cohabiting
- Divorced
- Widowed
- Separated
- Single
- Choose not to answer

4. Do you live in Kigali?

- Yes
- No (Skip to Question #6)
- Choose not to answer (Skip to Question #6)

5. In what area in Kigali City Province do you live?

- Nyarugenge
- Kicukiro
- Gasabo urban (e.g., Kacyiru, Kimironko, Kinyinya, etc.) Gasabo rural (e.g., Nduba, Jabana, Gikomero, etc.)
- Do not know

Choose not to answer

6. Who do you live with? (Check all that apply)

- Live alone
- Partner/spouse
- Daughter(s)/son(s)
- Parents and/or other family
- Other: _____

7. What is your primary occupation?

- Student
- Employed by government, another institution, or company
- Self-employed (Small and medium enterprises)
- Self-employed (High income earnings)
- Unemployed/Do not work
- Other (specify): _____
- Choose not to answer (Skip to Question #8)

The following questions are sensitive and personal in nature. Your answers will be kept confidential. You may choose not to answer certain questions. Answering any question is voluntary

B. Parity

8. What age did you have your first full term birth ? __ (Year) (Enter 00 if refuse to answer, enter 99 if never pregnant or not yet had a pregnancy that resulted in a full term birth – i.e. all pre-term deliveries) (if 00 or 99, skip to Question #11)

9. How many full term births have you had in your lifetime? _____

10. Have you given birth in the last year?

- Yes
- No
- Choose not to answer

C. Contraceptive Use

11. Have you ever used Jadelle (contraceptive)?

- Never

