- No (Skip to Question #13)
- Choose not to answer (Skip to Question #13)

12. Do you currently use Jadell (contraceptive)?

- Yes
- No
- Choose not to answer

13. Have you ever used oral contraceptives?

- Yes
- No (Skip to Question #15)
- Choose not to answer (Skip to Question #15)

14. Do you currently use oral contraceptives?

- Yes
- No
- Choose not to answer

15. Have you ever used Depo Provera (contraceptive)?

- Yes
- No (Skip to Question #17)
- Choose not to answer (Skip to Question #17)

16. Do you currently use Depo Provera (contraceptive)?

- Yes
- No
- Choose not to answer

17. Do use condoms as a contraceptive?

- Yes
- No (skip to Question #19)
- Choose not to answer (skip to Question #19)

18. Have you used condoms as a contraceptive in the last 6 months?

- Yes
- No
- Choose not to answer

19. Have you ever used another contraceptive method?

- Yes. Please specify: _____
- No (skip to Question #21)
- Choose not to answer (skip to Question #21)

20. Do you currently use another contraceptive method?

- Yes. Please specify: _____
- No
- Choose not to answer

D. Sexual Behaviors

This last section of the questionnaire contains questions about sexual practices you may have engaged in over the years. This will help us understand your likelihood of having been exposed to human papillomavirus (HPV).

21. How many men have you had vaginal sex with, in your lifetime until now? Vaginal sex is a man inserting his penis into your vagina.

- No Men (Skip to question #25)
- 1 Man
- 2-3 Men
- 4-5 Men
- 6 or more Men
- Choose not to answer

22. How old were you when you first had vaginal sex? __ (Year) (Enter 00 if refuse to answer)

23. How many men have you had vaginal sex with in the last 6 months?

- No Men (Skip to Question #25)
- 1 Man
- 2 or more Men

Choose not to answer

24. In the past 6 months, how often has he used a condom during vaginal intercourse?

Never
 Occasionally
 Half the time
 Almost always
 Always

25. Have you ever had anal intercourse? Anal intercourse is a man inserting his penis into your anus/rectum.

Yes
 No (Skip to Question #29)
 Choose not to answer (Skip to Question #29)

26. How many men have you had anal sex with, in your lifetime until now?

1 Man
 2-3 Men
 4-5 Men
 6 or more Men
 Choose not to answer

27. How many men have you had anal sex with, in the past 6 months?

No Men (Skip to Question #29)
 1 Man
 2 or more Men
 Choose not to answer

28. In the past 6 months, how often has he used a condom during anal sex?

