APPENDIX IV. FOLLOW UP QUESTIONNAIRE

Thank you for agreeing to participate in our study. This interview should take no more than 10 minutes. These questions are personal about your sexual history. All your answers are strictly confidential, and it is very important for us that you try to answer all the questions as openly as possible, even if they are a little uncomfortable or embarrassing. This information will be important in understanding how the HPV vaccine protects women against HPV infection. If you don't understand any of the questions, please inform the study nurse who will try to help explain them. You should also be aware that you have a right not to respond to any question with which you are uncomfortable.

1. What is your date of birth? DD/ MM /YYYY (enter all 0 if not remembered)

__ / __ / __ __

2. What is your age? __ (Year)

The following questions are sensitive and personal in nature about sexual practices you may have engaged in since your last study visit. This will help us understand your likelihood of having been newly exposed to human papillomavirus (HPV). Your answers will be kept confidential. You may choose not to answer certain questions. Answering any question is voluntary.

3. Since your last visit, how many men have you had vaginal sex with?

- No Men
- 1 Man
- 2 or more Men
- Choose not to answer

4. Since your last visit, how many men have you had anal sex with?

- No Men
- 1 Man
- 2 or more Men
- Choose not to answer

5. Since your last visit, how many men have you performed oral sex on?

- No Men
- 1 Man
- 2 or more Men

Choose not to answer

END OF QUESTIONNAIRE

REFERENCES

1. Rwanda Population-Based HIV Impact Assessment. October 2019.
2. IGC-O. GLOBOCAN 2018 database. 2018.
3. Cervix Cancer Screening. IARC. 2005;10.
4. Kitchener HC, [name] PE, Cox JT. Chapter 7: Achievements and limitations of cervical cytology screening. *Vaccine*. 2006 Aug 31;24 Suppl 3:S3/63-70. PubMed PMID: 16950019. Epub 2006/09/05.
6. Centers for Disease Control and Prevention. 1993 revised classification system for HIV infection and expanded surveillance case definition for AIDS among adolescents and adults. *JAMA*. 1993;269(6):729-30.

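### Enrollment item 11 has no affirmative answer for implant use, and the follow-up form counts partners without asking whether any of them is new

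*Combined protocol and SAP*

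**What the plan says.** Appendix III, item 11, asks "Have you ever used Jadelle (contraceptive". The answers printed are *Never*, then "No (Skip to Question #13", then a refusal that also skips to item 13. Item 12 asks "Do you currently use Jadell (contraceptive" and offers *Yes*, *No* or a refusal. The next ever-use item, "Have you ever used oral contraceptives", offers *Yes*, *No* with a skip, and a refusal with a skip; item 15 on Depo Provera has the same layout. Section VI.F.1.a has the questionnaire run by ACASI, with the nurse helping only on request.

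Appendix IV introduces its partner items with this purpose: "This will help us understand your likelihood of having been newly exposed to human papillomavirus (HPV". Item 3 then asks "Since your last visit, how many men have you had vaginal sex with"; items 4 and 5 do the same for anal and oral sex. Each offers *No Men*, *1 Man*, *2 or more Men* or a refusal.

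Section VI.A sets the use of the second visit: "Participants positive for high-risk HPV and/or HPV6/11 on any sample will have a 6-12 month follow-up visit to measure HPV type-specific persistence". Section VII.A.1 allows additional models that adjust for sexual behaviors, among other factors. Section VII.C will examine "other risk factors (e.g., sexual behaviors) on whether HPV infection persists vs. clears".

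**The concern.** Two items do not deliver the information they are there to collect.

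Item 11 gives a past implant user no truthful answer and sends a current user to item 12 only if she first denies ever using the implant. Women who never used it may pick either *Never* or *No*. *Never* can thus hold both never-users and users looking for the way forward.

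The follow-up form claims to capture new exposure but records only the number of partners. A woman with the same partner throughout and a woman who changed to one new partner give the same answer. Persistence at 6-12 months is a main outcome, and the plan itself expects sexual behavior to differ between its groups (Section VII.A.1). Finding the same type at two visits is compatible with one continuing infection or with clearance followed by re-infection. New partners in the interval are the obvious variable for probing that, and the form does not ask for them.

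**Working it through.** No formula in the plan bears on the wording of the forms, so the check is mainly of text.

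**Step 1. Ever-use items side by side (Appendix III).**

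| Item | First answer | Second | Third | Affirmative answers | Answer leading to the current-use item |
|---|---|---|---|---|---|
| 11, Jadelle | *Never* | *No*, skip to 13 | Refusal, skip to 13 | 0 of 3 | *Never* |
| 13, oral contraceptives | *Yes* | *No*, skip to 15 | Refusal, skip to 15 | 1 of 3 | *Yes* |
| 15, Depo Provera | *Yes* | *No*, skip to 17 | Refusal, skip to 17 | 1 of 3 | *Yes* |

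*Never* sits exactly where *Yes* belongs, and it is the only answer without a skip. A substituted word explains this better than a missing fourth line.

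**Step 2. What item 11 can still yield.** A current user who answers *Never* and then *Yes* at item 12 is identifiable as a current, and so ever, user. A past user is not identifiable by any route through items 11 and 12.

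**Step 3. Can a new partner be derived from other items?** The baseline form has a lifetime count in bands (item 21) and a count for the past six months (item 23). The follow-up count covers the interval since baseline, which Section VI.F.2 allows to run from 5 to 15 months. The lifetime count is not repeated. For vaginal sex:

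| Follow-up answer | What follows |
|---|---|
| *No Men* | No reported exposure by this route |
| *1 Man* | New by this route only if the baseline lifetime count was none; otherwise undetermined |
| *2 or more Men* | At least one new only if the baseline lifetime count was none or one; otherwise undetermined |

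Comparing with item 23 does not settle the undetermined cells: one man in the six months before baseline and one man afterwards may or may not be the same man. So 3 partner-count items yield 0 direct measures of a new partner, and *1 Man* stays mixed for nearly every baseline history.

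**Step 4. Does the form enter the endpoint?** Persistence is type-specific HPV at baseline and again at follow-up, at sites positive at baseline (Sections VI.A and VI.F.2). No questionnaire answer is part of it.

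**Step 5. How many women could be re-asked item 11?** Section X.A.2 expects about 30% of the 3,028 participants to be invited to follow-up: 0.30 × 3,028 ≈ 908. With the 10% loss assumed in Section VII.A.2, 0.90 × 908 ≈ 817 would be seen. Women negative at all three sites, 3,028 − 908 = 2,120 on the same assumption, leave after enrollment and cannot be re-asked at a study visit.

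**The case against.** The best case for the plan has four parts.

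- *The printed form may not be the fielded one.* The questions are given by audio in Kinyarwanda (Section IX.D), and piloting and instrument development are planned (Section IX.E). An answer line could also have been lost in text extraction. This stands as a reason to check the source PDF and the programmed form first. It does not explain why *Never* occupies the *Yes* position.
- *Implant use matters little to the stated analyses.* Section VII names no contraceptive covariate, and items 19-20 take other methods as free text. The first part stands, so a claim that planned models are damaged would go too far. Free text is a weak backstop, because it asks about methods other than those already listed.
- *The Aim 1 measure already handles exposure.* Section VII.A.1 compares targeted with untargeted types within each group so that differences in exposure largely cancel. This stands in part: neither the plan nor this check shows residual bias in that odds ratio. The argument does not carry over to Section VII.C, which models persistence against clearance directly and lists sexual behavior as a candidate determinant.
- *The partner counts are informative.* True for *No Men* and for the few combinations in Step 3, but not for *1 Man* in general.

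A reader might infer that the form makes re-exposure pass as persistence. The documents do not support that: the two-visit definition creates the ambiguity, and a new-partner item would reclassify no infection. A reader might also infer that treatment between visits is being counted as clearance. The remark in Section X.A.2 about seeking services elsewhere concerns women who do not wish to participate. Prior treatment for cervical abnormalities is an exclusion (Section VI.D.2), and eligibility is confirmed again at follow-up (Section VI.F.2).

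**Conclusion.** The point holds in a limited form. As printed, item 11 cannot record past implant use truthfully and reaches current use only through a contradictory answer. The follow-up form does not separate a new from a continuing partner, although gauging new exposure is its stated purpose.

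The consequence is lost information. No infection is misclassified because of either form. Without a new-partner item, the persistence analyses cannot adjust for or examine new exposure, apart from setting aside women who report *No Men* and the few derivable combinations. The effect on prevalence, persistence or any odds ratio cannot be sized, because the documents give neither implant use nor partner change.

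The conclusion assumes that the printed Appendix III matches what is programmed; if the fielded item 11 already offers *Yes*, that half reduces to a correction of the document. The follow-up half rests on the wording of Appendix IV alone.

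**What to change.** **Item 11.** Check the source PDF and the programmed Kinyarwanda ACASI form, then replace *Never* with *Yes*. If the faulty version has been used:

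- keep *Yes* answers at item 12 as current use;
- set ambiguous ever-use answers to missing, in particular *Never* without a *Yes* at item 12;
- state in advance how *No* is treated, since some users may have chosen it for want of a truthful answer;
- re-ask at follow-up where a visit takes place, accepting that women negative at all sites cannot be recovered this way.

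**Appendix IV.** After each of items 3, 4 and 5, ask how many of these men were new partners since the last visit, skipping it for women who report *No Men*.

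**Sections VII.A.1 and VII.C.** Keep the persistence definition. Add a prespecified sensitivity analysis of type-specific persistence in women reporting no new partner, with the number of women in it. State that it does not exclude re-exposure from a continuing partner.

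**Cost.** About one extra minute per follow-up visit, on a form announced as taking no more than 10, plus a form amendment and one further analysis. The sensitivity analysis will use fewer women and be less precise than the main one. New-partner data not collected at the visit will be hard to recover later, so the change is worth most if made before follow-up visits begin.

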APPENDIX IV. FOLLOW UP QUESTIONNAIRE

Thank you for agreeing to participate in our study. This interview should take no more than 10 minutes. These questions are personal about your sexual history. All your answers are strictly confidential, and it is very important for us that you try to answer all the questions as openly as possible, even if they are a little uncomfortable or embarrassing. This information will be important in understanding how the HPV vaccine protects women against HPV infection. If you don't understand any of the questions, please inform the study nurse who will try to help explain them. You should also be aware that you have a right not to respond to any question with which you are uncomfortable.

1. What is your date of birth? DD/ MM /YYYY (enter all 0 if not remembered)

__ / __ / __ __

2. What is your age? __ (Year)

The following questions are sensitive and personal in nature about sexual practices you may have engaged in since your last study visit. This will help us understand your likelihood of having been newly exposed to human papillomavirus (HPV). Your answers will be kept confidential. You may choose not to answer certain questions. Answering any question is voluntary.

3. Since your last visit, how many men have you had vaginal sex with?

- No Men
- 1 Man
- 2 or more Men
- Choose not to answer

4. Since your last visit, how many men have you had anal sex with?

- No Men
- 1 Man
- 2 or more Men
- Choose not to answer

5. Since your last visit, how many men have you performed oral sex on?

- No Men
- 1 Man
- 2 or more Men

Choose not to answer

END OF QUESTIONNAIRE

REFERENCES

1. Rwanda Population-Based HIV Impact Assessment. October 2019.
2. IGC-O. GLOBOCAN 2018 database. 2018.
3. Cervix Cancer Screening. IARC. 2005;10.
4. Kitchener HC, [name] PE, Cox JT. Chapter 7: Achievements and limitations of cervical cytology screening. *Vaccine*. 2006 Aug 31;24 Suppl 3:S3/63-70. PubMed PMID: 16950019. Epub 2006/09/05.
6. Centers for Disease Control and Prevention. 1993 revised classification system for HIV infection and expanded surveillance case definition for AIDS among adolescents and adults. *JAMA*. 1993;269(6):729-30.
